#### 3.3 Known and Potential Risks and Benefits to Human Subjects

[figure not shown]
Aramchol is a novel fatty acid-bile acid conjugate targeted to the liver that induces beneficial modulation of intrahepatic lipid metabolism. In non-clinical studies, the effect of Aramchol on fibrosis was shown to be indirect via reduction of steatosis and ballooning, and direct via reduction of collagen production from human HSC.

In the Phase 2b ARREST study, Aramchol 600mg once daily showed potential efficacy on the two biopsy endpoints that may currently constitute a primary endpoint for a Phase 3 study; NASH resolution and no fibrosis worsening as well as Improvement in Fibrosis and no NASH worsening.

In this one-year study, in patients with NASH and comorbidities, both doses of Aramchol showed a favorable safety and tolerability profile. No death was reported in the study. SAEs were reported in approximately 10% of subjects. Each SAE was reported for a single subject, and SAEs were typical for the patient population. No clustering of event types was noted in the active-treatment arms. The leading causes for ET were consent withdrawal and AEs. The incidence of ET due to AEs was very low and similar across study arms.

Most AEs in the study were mild and recovered. The proportion of severe events was overall low in all treatment arms and no differences were noted in incidence of severe AEs between arms.

The study design employs risk-mitigation measures, with extensive safety monitoring that includes recording and monitoring of adverse events, safety laboratories, vital signs and physical examinations as well as stopping rules and special warnings and precautions for use. The study will be followed by a DMC that will assess the ongoing safety during the study as well as independent adjudication committees for clinical out-come events, possible DILI events and major adverse cardiovascular events (MACE).

# 3.4 Rationale for Study Design, Dose and Population

#### 3.4.1 Study Rationale

The current study is composed of two parts:

An Open-Label Part to evaluate the safety and PK of Aramchol 300 mg BID in subjects with NASH and liver fibrosis and to explore the kinetics of histological outcomes and NITs associated with NASH and liver fibrosis for the treatment duration of 24, 48 and 72 weeks. The study population includes subjects with NASH and liver fibrosis stage 1-3, subjects with NASH who may or may not be overweight and subjects with NASH who may or may not have T2DM or be pre-diabetic. PK and safety data and information on the kinetics of histological outcomes and NITs from this Open-label Part will be summarized in support of regulatory submissions. However, histological outcomes and clinical events from the Open-Label Part will not be considered for the Histology-Based primary endpoint and the Clinically-Based primary

endpoint of the Randomized, Double-Blind, Placebo-controlled part of the study. Clinical events will instead be reported as safety data.

A Randomized, Double-Blind, Placebo-Controlled Part to evaluate the safety and efficacy of Aramchol 300 mg BID to support regulatory approval. The study population for this part includes subjects with NASH and liver fibrosis stage 2 and 3 who are overweight and are either pre-diabetic or have T2DM. The Randomized, Double-blind, Placebo-Controlled Part of the study is generally consistent with FDA Guidance for Industry – Noncirrhotic Nonalcoholic Steatohepatitis with Liver Fibrosis: Developing Drugs for Treatment (December 2018) 13 and EMA Reflection paper on regulatory requirements for the development of medicinal products for chronic noninfectious liver diseases (PBC, PSC, NASH) (November 2018)14, and is intended to demonstrate the effectiveness and safety of Aramchol to support regulatory approval. Consistent with regulatory guidance there are two primary endpoints for this part of the study:

- ✓ A Histology-Based primary endpoint that will be analyzed after 1000 subjects have completed 72 weeks. The Histology-Based endpoint data will serve as the basis for the submission of a marketing authorization application under regulatory provisions of accelerated/conditional approval based on a surrogate endpoint.
- ✓ The Clinically-Based primary endpoint that will be analyzed at EoS and will provide confirmation of clinical benefit based on a clinical outcomes endpoint.

✓ The open label part of the study will provide additional safety and PK information for Aramchol 300 mg BID in subjects with NASH while enrollment in the Randomized, Double-

blind, Placebo-controlled Part of the study is pending. Long-term safety data from this study will ultimately be a valuable addition to Aramchol safety database.

The kinetics of histological outcomes and NITs for NASH associated with liver fibrosis have not been well characterized for NASH (e.g. how early can a beneficial effect on fibrosis be observed, are there subjects that improve with longer duration of therapy etc.). Phase 2 NATIVE study with lanifibranor, cohort 4 in the Phase 2 study with aldafermin, BALANCED Phase 2a study with efruxifermin) suggest that favorable effects may be observed as early as at week 16; other studies have reported longer times to observed effect including up to 96 weeks in the PIVENS study with pioglitazone. However, no study, yet, has examined within one clinical setting the kinetics of histological outcome measures for the different treatment duration. The Phase 2b ARREST study had a 52-week endpoint for which favorable effects were observed. However, it is not known how early a treatment effect may be observed and what the difference may be for histological outcomes and NITs between a treatment duration of 24, 48 or 72 weeks. The Open-Label Part will provide data to help characterize the kinetics of histological outcomes and NITs for Aramchol.

3.4.2

# 3.4.3 Study Population Rationale

Patients with stage 2-3 fibrosis, who are overweight/obese with prediabetes or type 2 diabetes are considered at greatest risk for the negative outcomes of NASH. Features of metabolic syndrome (MetS) are not only highly prevalent in patients with NAFLD, but components of MetS also increase the risk of developing NAFLD. This bidirectional association between NAFLD and components of MetS has been well established. In addition, the presence of an increasing number of metabolic diseases, such as insulin resistance, type 2 diabetes, hypertension, dyslipidemia, and visceral obesity, seems to increase the risk of progressive liver disease. Therefore, patients with NAFLD and multiple risk factors such as type 2 diabetes and hypertension are at the highest risk for adverse outcomes

The Randomized, Double-Blind, Placebo-Controlled Part will enroll adult subjects, 18–75 years old, with NASH and fibrosis (F2-F3) confirmed by liver histology who are overweight or obese and have prediabetes or type 2 diabetes.

The Open-label Part intends to assess the safety, PK and treatment response kinetics of Aramchol 300mg BID in a broader population, including subjects with fibrosis stage 1, subjects who are not overweight, and subjects who do not have T2DM.

In both study parts, patients with cirrhosis, abnormal synthetic liver function and history or presence of decompensated liver disease will not be enrolled to the study.

#### 4 STUDY OBJECTIVES

#### Open-Label Part:

- To evaluate the safety and PK of twice daily administration (BID) of Aramchol 300mg in subjects with NASH and liver fibrosis.
- To explore the kinetics of histological outcome measures and Non-Invasive Tests (NITs)
  associated with NASH and fibrosis for the treatment duration of 24, 48 and 72 weeks.

#### Randomized, Double-Blind, Placebo-Controlled Part:

To evaluate the efficacy and safety of twice daily administration (BID) of Aramchol 300mg as compared to placebo in subjects with NASH and liver fibrosis.

#### 4.1 Efficacy Endpoints

#### 4.1.1 Open-Label Part

# **Primary kinetics Endpoints:**

The primary endpoints are the kinetics of the following histological outcome measures for treatment duration of 24, 48 and 72 weeks and potentially following a 2nd post-baseline biopsy at weeks 72 or 96 or 120, respectively:

- Improvement in Fibrosis defined as the Proportion (%) of subjects with improvement in liver fibrosis greater than or equal to one stage (NASH CRN fibrosis score) and no worsening of steatohepatitis (defined as no increase in NAS for ballooning, inflammation or steatosis)
- Resolution of NASH defined as the Proportion (%) of subjects with resolution of NASH (defined by ballooning of 0 and inflammation 0-1) and no worsening of liver fibrosis on NASH CRN fibrosis score (≥ 1 stage increase).

#### Secondary kinetics Endpoints:

The secondary endpoints are the kinetics of the following parameters and NITs for the treatment duration of 24, 48 and 72 weeks:

- ALT and AST
- Glycemic parameters
- Lipid parameters
- Fibroscan
- Biomarkers including but not limited to ProC3 and ELF
- Microbiome profile

#### 4.1.2 Randomized, Double-Blind, Placebo-Controlled Part

#### **Primary Efficacy Endpoints**

The primary efficacy endpoints of the Randomized, Double-Blind, Placebo-Controlled Part are:

- 1. Histology-Based: The Histology-Based primary endpoint will be derived from the week 72 biopsy of the initial 1000 subjects as compared to baseline biopsy and will use:
  - ✓ Resolution of NASH defined as the Proportion (%) of subjects with resolution of NASH (defined by Ballooning of 0 and inflammation 0-1) and no worsening of liver fibrosis on NASH CRN fibrosis score (≥ 1 stage increase).

OR

- ✓ Improvement in Fibrosis defined as the Proportion (%) of subjects with improvement in liver fibrosis greater than or equal to one stage (NASH CRN fibrosis score) and no worsening of steatohepatitis (defined as no increase in NAS for ballooning, inflammation or steatosis)
- 2. Clinically-Based: The Clinically-Based primary endpoint is time to first occurrence of any of the following adjudicated events
  - ✓ All-cause mortality
  - ✓ Liver transplant
  - ✓ Histological progression to cirrhosis
  - ✓ MELD score >15 if baseline MELD score was <12

- ✓ Hospitalization due to hepatic decompensation event(s) including:
  - Hepatic encephalopathy grade ≥2 (as assessed by West Haven scale)
  - Variceal bleeding
  - New onset ascites requiring treatment
  - Spontaneous bacterial peritonitis as assessed by either positive cell culture or cell count

Events will be adjudicated by the independent Clinical Outcome Adjudication Committee (COAC).

# **Key Secondary Efficacy Endpoints**

The key secondary efficacy endpoint for the Randomized, Double-Blind, Placebo-Controlled Part is:

At EoS, **Improvement in Fibrosis:** 5-Year Proportion (%) of subjects with improvement in liver fibrosis greater than or equal to one stage (NASH CRN fibrosis score) and no worsening of steatohepatitis (defined as no increase in NAS for ballooning, inflammation or steatosis).

## **Exploratory Endpoints**

#### 4.2 Safety and Tolerability Evaluations

- Adverse events and serious adverse events.
- 2. Safety laboratory evaluations.
- 3. Vitals signs.
- 12-Lead ECG.
- 5. Physical examinations.
- 6. Drop-out rates.

# 4.3 Pharmacokinetic Endpoints

Plasma concentrations of Aramchol will be subjected to population pharmacokinetic analysis using NONMEM software. In addition to variability in the whole population that have received treatment with Aramchol, the relationships between the population PK profiles and factors such as demography, duration of treatment, concomitant medications, severity of disease and response to treatment will be examined.

#### 5 STUDY DESIGN

#### 5.1 Overview and Plan

The current study includes two parts:

#### Open-Label Part:

A total of 150 subjects including those already randomized to Aramchol 300mg BID or placebo, will be randomized in a ratio of 1:1:1 to receive Aramchol 300mg BID according to the below grouping:

- Group A: The post-baseline liver biopsy will be conducted at week 24
- Group B: The post-baseline liver biopsy will be conducted at week 48
- Group C: The post-baseline liver biopsy will be conducted at week 72

In order to more comprehensively explore the kinetics of histological outcome measures (e.g. are there subjects who may not show improvement in outcome at week 24, 48 or 72 but may improve with longer duration of treatment), a 2nd post-baseline liver biopsy sample will be collected for subjects whose post-baseline liver biopsy at week 24 or 48 or 72 does not show at least 1 stage improvement in fibrosis (fibrosis non-responders). The 2nd post-baseline liver biopsy sample will be collected 1 year later (i.e. at weeks 72 or 96 or 120 respectively

Subjects already randomized and ongoing in the Randomized, Double-Blind, Placebo-Controlled Part in the selected sites participating in the Open-Label part will be given the option to switch to the Open-Label Part.

The Open-Label Part will continue for the same duration than the Randomized, Double-Blind, Placebo-Controlled Part. All subjects in the Open-Label Part will receive Aramchol 300mg BID until EoS.

The study schema of the Open-Label Part is presented in Figure 1

Figure 1: Open-Label Part Schema

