	An Open-Label Part to evaluate the safety and PK of Aramchol 300 mg BID in subjects with NASH and liver fibrosis and to explore the kinetics of histological outcomes and NITs associated with NASH and liver fibrosis for the treatment duration of 24, 48 and 72 weeks. The study population includes subjects with NASH and liver fibrosis stage 1-3, subjects with NASH who may or may not be overweight and subjects with NASH who may or may not have T2DM or be pre-diabetic. PK and safety data and information on the kinetics of histological outcomes and NITs from this Open-Label Part will be summarized in support of regulatory submissions. However, histological outcomes and clinical events from the Open-Label Part will not be considered for the Histology-Based primary endpoint and the Clinically-Based primary endpoint of the Randomized, Double-Blind, Placebo-controlled part of the study. Clinical events will instead be reported as safety data.
	A Randomized, Double-Blind, Placebo-Controlled Part to evaluate the safety and efficacy of Aramchol 300 mg BID to support regulatory approval. The study population for this part includes subjects with NASH and liver fibrosis stage 2 and 3 who are overweight and are either pre-diabetic or have T2DM. The Randomized, Double-blind, Placebo-Controlled Part of the study is generally consistent with FDA Guidance for Industry – Noncirrhotic Nonalcoholic Steatohepatitis with Liver Fibrosis: Developing Drugs for Treatment (December 2018) and EMA Reflection paper on regulatory requirements for the development of medicinal products for chronic noninfectious liver diseases (PBC, PSC, NASH) (November 2018), and is intended to demonstrate the effectiveness and safety of Aramchol to support regulatory approval.

[figure not shown]
✓ The open label part of the study will provide additional safety and PK information for Aramchol 300 mg BID in subjects with NASH while enrollment in the Randomized, Double-blind, Placebo-controlled Part of the study is pending. Long-term safety data from this study will ultimately be a valuable addition to Aramchol safety database.

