#### **Principal Analysis Set for Efficacy Inference:**

The principal analysis set for efficacy inference will be the Intention-to-Treat (ITT) Analysis Set which will include all randomized subjects as follows:

- The Histology-Based primary endpoint will employ the Histology-Based-ITT Analysis Set including all initially 1000 randomized subjects.
- The Clinically-Based primary endpoint will employ the Clinically-Based-ITT Analysis Set including all randomized subjects.

[figure not shown]

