#### Early discontinuation

There are two types of early discontinuation:

- Early Treatment Discontinuation (ETD): Subject discontinues treatment but continues with the scheduled visits.
- Early Study Discontinuation (ESD): Subject discontinues study.

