## 11.2.8 Primary Estimands of Interest

## 11.2.8.1 Week-72 Histology-Based Primary Estimand

The primary Estimand for the Week-72 Histology-Based study part will be based on the effectiveness assumption (de-facto) using treatment policy. The primary Estimand construction elements of this Estimand are:

- Population: Subjects with Nonalcoholic Steatohepatitis (NASH) that were randomized to the study.
- Variables of interest: Week-72 (-2 Weeks, +6 Weeks) individual subject Resolution of NASH, OR, Improvement in Fibrosis.
- 3. Inter-current events: Subjects that ESD during the Histology-Based study part. The treatment-policy Estimand will be used to assess the benefit of Aramchol as compared to

- placebo in initially randomized subjects' as actually observed regardless of the occurrence of ESD during the Histology-Based study part.
- Population-level summary: The between groups difference in the proportion of subjects
  with NASH Resolution AND/OR the between groups difference in the proportion of subjects
  with Improvement in Fibrosis.

The treatment effect will be attributable to the subject's with NASH initially randomized to the study and who had the baseline and Week-72 liver biopsies regardless of ESD during the Histology-Based study part.

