#### 11.2.8.2 EoS Clinically-Based Primary Estimand

The primary Estimand for the EoS Clinically-Based study part will be based on the effectiveness assumption (de-facto) using treatment policy. The primary Estimand construction elements are:

- Population: Subjects with Nonalcoholic Steatohepatitis (NASH) that were randomized to the study.
- 2. Variables of interest: Time to first occurrence of the adjudicated events.
- Inter-current event: Subjects that were early discontinued from the study (ESD). The
  treatment-policy Estimand will be used to assess the benefit of Aramchol as compared to
  placebo in initially randomized subjects' as actually observed regardless of the occurrence
  of ESD.
- 4. Population-level summary: The difference in survival distributions/percentiles observed in the Aramchol arm as compared to the Placebo Arm.

The treatment effect will be attributable to the subject's with NASH initially randomized to the study regardless of study early discontinuation.

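### For subjects who switch to open-label Aramchol, the primary analyses as visible do not match the stated treatment-policy estimands, and exposed switchers can be randomised to a biopsy week already past

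*Combined protocol and SAP*

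**What the plan says.** **The switch.** Under Section 5.1, repeated in Section 8.4.2, double-blind subjects "ongoing in the Randomized, Double-Blind, Placebo-Controlled Part in the selected sites participating in the Open-Label part will be given the option to switch" into open-label treatment, where everyone receives Aramchol. The Synopsis says the Open-Label Part will supply safety and PK data "while enrollment in the Randomized, Double-blind, Placebo-controlled Part of the study is pending".

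**Who is analysed.** The Synopsis defines the principal sets without a visible exception for switchers: "The Histology-Based primary endpoint will employ the Histology-Based-ITT Analysis Set including all initially 1000 randomized subjects", and "The Clinically-Based primary endpoint will employ the Clinically-Based-ITT Analysis Set including all randomized subjects".

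**Which data count.** The Synopsis rationale, repeated in Section 3.4.1, says that "histological outcomes and clinical events from the Open-Label Part will not be considered for the Histology-Based primary endpoint and the Clinically-Based primary endpoint" of the double-blind part. Clinical events from the Open-Label Part are reported as safety data instead.

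**The estimands.** Sections 11.2.8.1 and 11.2.8.2 both use treatment policy. The histology estimand takes outcomes "as actually observed regardless of the occurrence of ESD during the Histology-Based study part", and the clinical estimand is worded in the same way. ESD is the only intercurrent event named in either. Section 8.1 defines it in one line: "Early Study Discontinuation (ESD): Subject discontinues study". The cases for which Section 8.2.8 requires ESD do not include the switch.

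**Missing biopsies.** Section 11.2.9.2 handles missing week-72 values by deterministic rules together with multiple imputation. Its one example of a rule sets a subject with a clinical event before week 72 to failure. Detail is left to the SAP.

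**Open-label biopsy groups.** Sections 8.4.2 and 11.1 randomise all open-label subjects 1:1:1, switchers included, to a biopsy at week 24 (A), 48 (B) or 72 (C). They use semi-minimization with prior Aramchol exposure as one balancing factor. Under Section 8.1, switchers from Aramchol continue their running visit schedule and switchers from placebo restart at Baseline. Sections 8.2.3 and 9.1.1 give a biopsy window of 2 weeks before to 6 weeks after.

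**The concern.** A treatment-policy effect in the ITT population needs each subject's outcome after the intercurrent event. For a switcher, that later outcome is what the rationale sections discard. The analysis then rests on imputation for histology, and on uncounted follow-up for clinical events, while the estimand text describes something else. A reader of the histology result, which is meant to support accelerated or conditional approval, would be told it is a treatment-policy effect when for switchers it is not.

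The second issue is in the Open-Label Part. Its primary endpoints describe histology after 24, 48 and 72 weeks of treatment, so the group label is meant to stand for weeks on drug. A subject who arrives with months of prior Aramchol and a running clock can be assigned to a biopsy week that has already gone by.

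**Working it through.** **No plan figure to reproduce.** The sample size rationale (Section 11.2.5) is not in the visible text. The alpha split is consistent: 0.02 + 0.03 = 0.05.

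**Step 1. Follow one switcher with no week-72 biopsy before the switch.**
- The subject is in the ITT set as randomised.
- Any later biopsy comes from the Open-Label Part and is barred, so the week-72 value is missing and falls to Section 11.2.9.2.
- Any later clinical event is barred from the clinical endpoint and goes to safety.
- If the switch counts as ESD, treatment policy asks for outcomes that are barred.
- If it does not, the estimands say nothing about the switch, and the exclusion operates without an estimand to match it.

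On either reading the estimate for switchers is not the treatment-policy effect.

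**Step 2. Size for histology.** Assumptions:
- Phase 2b rates from Section 3.2: fibrosis improvement 29.5% vs 17.5%, NASH resolution 16.7% vs 5.0%.
- N = 1000 at 2:1.
- Lowest truncated Hochberg step, (0.1/2 + 0.9/2) × 0.02 = 0.01 two-sided.
- s switchers split 2:1, all among the first 1000 and all before their week-72 biopsy.

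The number of switchers is not given. The ceiling is 150, which leaves no place for a newly enrolled open-label subject. It is 120 if the 30 F1 places fill, because the double-blind part admits only F2–F3.

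Power = Φ[(d − 2.576 × SE0) / SE1], with SE0 pooled and SE1 unpooled. With s = 0 the pooled rate is 0.255, SE0 = 0.0292, SE1 = 0.0273, and (0.120 − 2.576 × 0.0292)/0.0273 = 1.64, giving 94.9%.

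Two handlings are compatible with the text: the value is lost (N × (1 − s/1000) at unchanged rates, approximating imputation under missing at random), or it is set to failure (both rates × (1 − s/1000)).

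| Switchers | Lost: difference, power | Failure: difference, power |
|---|---|---|
| 0 | 12.0 points, 94.9% | 12.0 points, 94.9% |
| 50 | 12.0, 93.6% | 11.4, 93.2% |
| 100 | 12.0, 92.1% | 10.8, 91.1% |
| 150 | 12.0, 90.2% | 10.2, 88.4% |

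Using the unpooled error throughout, power starts at 96.6% and at 150 switchers is 93.0% (lost) or 91.8% (failure). NASH resolution, pooled, goes from 99.9% to 99.6% at 150 switchers under either handling.

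**Step 3. Size for the clinical endpoint.** At an average risk of 380/2000 = 19%, switchers would carry 50 × 0.19 = 9.5, 100 × 0.19 = 19 or 150 × 0.19 = 28.5 events over the whole study. That is 2.5%, 5% or 7.5% of 380. Only the post-switch share of these is affected.

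**Step 4. Biopsy windows for exposed switchers.** On the continuing clock the windows are:
- Group A: 24 − 2 to 24 + 6, weeks 22–30.
- Group B: weeks 46–54.
- Group C: weeks 70–78.

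After week 30 Group A is closed, after week 54 Groups A and B are closed, and after week 78 all three are. No visible rule removes a closed group from the randomisation. If the clock instead restarted at the switch, a subject with w prior weeks on Aramchol would have the Group A biopsy at about w + 24 weeks on drug (64 weeks if w = 40). The label would then not equal treatment duration. Exposed switchers up to week 30 and placebo switchers, who restart, are not affected.

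**The case against.** The best defence is that the default can be derived. Open-label outcomes are barred, so a switcher's missing biopsy goes to Section 11.2.9.2 and post-switch clinical events do not count. Treatment policy is stated only for ESD, so on a strict reading the estimands are silent about the switch. Much of this stands: the data handling is largely determined by the text. What it does not supply is an estimand that describes the result, a censoring rule, or a statement on the count of 380.

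A rule may also sit in text that is not visible: Sections 11.2.3 to 11.2.6, most of 11.2.9.3, part of 11.1, or the separate SAP. That is a real limit on the point.

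Three stronger readings are tempting, and the documents do not support them:
- A reader might infer that the plan leaves open whether post-switch clinical events count in the primary analysis. The Synopsis and Section 3.4.1 exclude them.
- A reader might take pooled fibrosis power to fall as low as 82.5%. That figure needs 150 switchers, their post-switch outcomes counted, and placebo switchers responding fully like Aramchol. The plan forbids using those outcomes.
- A reader might forecast that a third, two-thirds or all of the late exposed switchers land in a closed group. Allocation is by semi-minimization, not simple equal chance, and the timing of switches is unknown.

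On the second issue, the Open-Label Part is declared exploratory, and an exposed switcher past week 78 was already scheduled for a double-blind week-72 biopsy with the same exposure as Group C. Both points lower the stakes. Neither supplies a rule.

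**Conclusion.** The concern holds in limited form and should be fixed; confidence is medium because relevant sections are not shown. For switchers, the visible passages keep the subject in the ITT set, discard the subject's later outcomes, and still label the estimand treatment policy. They must be reconciled.

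The effect on power is modest: under handling the text allows, about 1.3 to 1.7 points for fibrosis with 50 switchers (94.9% to 93.6% or 93.2%) and 4.7 to 6.5 points at the ceiling (to 90.2% or 88.4%). NASH resolution barely moves, so the chance of winning on at least one alternative changes little. These figures rest on Phase 2b rates and an assumed number and timing of switches. That switchers would come early enough to lack a week-72 biopsy is plausible from the stated timing of the Open-Label Part, but it is an inference.

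The allocation issue is secondary. On either reading of the clock, the group label can fail to describe weeks on Aramchol for late exposed switchers.

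**What to change.** **Double-blind analyses.** Keep switchers in both ITT sets as randomised, and name the switch in both estimands as an intercurrent event separate from ESD.
- *Histology:* use an in-window biopsy taken before the switch if there is one; otherwise use the multiple imputation of Section 11.2.9.2. State that this targets the outcome had the subject stayed in the double-blind part. Add a sensitivity analysis with failure imputed.
- *Clinical endpoint:* state that follow-up is censored at the switch, consistent with the Synopsis and Section 3.4.1, and that post-switch events do not count toward the 380. Add a sensitivity analysis that counts them as randomised.
- Report the number and timing of switches by arm.

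**Open-label allocation.** Randomise exposed switchers only among groups whose biopsy window is still open. State how those past week 78 enter the kinetics analysis, for example through their double-blind week-72 biopsy if one was taken. Analyse kinetics by actual cumulative weeks on Aramchol at biopsy.

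If the sections not shown or the SAP already hold a switcher rule, align the Synopsis and Sections 3.4.1, 8.4.2, 11.1 and 11.2.8 with it.

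**Cost.** Wording, which can go into the SAP amendment that Section 8.4.3 already plans before the histology unblinding, plus one restriction in the allocation algorithm. No extra biopsies are needed. The histology result for switchers will rest on a missing-at-random assumption. The open-label groups become slightly unequal, and their randomised comparison less clean, in an exploratory part.
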